8.1 Physical examination

A complete physical examination will be performed during screening (<4 weeks prior to study enrollment). Physical exam will include:

- Abdominal examination
- Weight
- Height (at screening only)
- ECOG performance status

Abnormal physical examination findings during screening will be captured as medical history. Abnormal physical examination findings observed after signing of the informed consent will be recorded as adverse events (AEs).

8.2 Laboratory assessment

The following studies and laboratory tests will be completed within 0-14 days prior to colesevelam treatment:

- Complete blood count with differential count
- Comprehensive metabolic panel: sodium, potassium, chloride, carbon dioxide, serum creatinine, glucose, blood urea nitrogen (BUN), EGFR, albumin, calcium, magnesium, phosphorus, alkaline phosphatase, ALT, AST, total bilirubin, direct bilirubin, uric acid, LDH, total protein
- Serum protein electrophoresis (SPEP) and serum immunofixation to assess for presence and quantity of monoclonal protein (M-protein)
- Serum free light chain studies
- Quantitative immunoglobulins
- Serum triglycerides

8.3 Stool studies

Patients will have stool studies during screening (within 14 days before first dose of colesevelam)

Stool studies should include:

- Stool bacterial culture
- Stool *Clostridium difficile* toxin PCR when clinically indicated, thus in liquid but not formed stool samples.
- Stool ova and parasite examination
- Stool Giardia and Cryptosporidium antigen tests
- Stool sample collection for microbiota is optional if this is not already performed

Each physician should consider and rule out diarrhea cause by medications, especially if the medication has been started recently. Medications more likely to cause diarrhea include, magnesium-containing antacids and laxatives, sugar alcohols (e.g. mannitol, sorbitol, xylitol), antibiotics, metoclopramide, stimulant laxatives, acarbose, orlistat, metformin, immunosuppressants, and tricyclic antidepressants.

8.4 Diarrhea assessments

Diarrhea assessments using the CTCAE scale will be performed at screening (within 7 days before dosing on Cycle 1 Day 1). Diarrhea will be assessed using the CTCAE grading for the primary endpoint. Frequency and consistency of bowel movements will be recorded using a diarrhea questionnaire (Appendix 2). The Bristol Stool Form Scale will be used to evaluate diarrhea and stool consistency (Appendix 3).

8.5 Assessment of gastrointestinal symptoms and diet

GI symptoms will be assessed at baseline using the GI oriented questions within PRO-CTCAE (Appendix 4). Diet will be recorded using a dietary questionnaire (Appendix 5).

8.6 Correlative analyses: Pharmacokinetic studies

Blood samples will be collected from up to 15 subjects for determination of plasma concentrations of lenalidomide at baselines as well as day 8 while on colesevelam. Blood samples for the determination of plasma concentration of lenalidomide will be obtained from each patient via 6mL sodium heparin (green top) tube collected prior to the first dose of colesevelam at the following time points: pre- colesevelam (day 1 baseline lenalidomide PK), 2 hours post- colesevelam on day 1, then additional pre- and 2 hours- post colesevelam samples on day 8. The 2-hours post colesevelam samples are alotted a window of +/- 30 minutes. It is crucial the patient record the time of their most recent lenalidomide dose from the prior evening in order to provide an accurate time since dose for accurate PK comparisons both between historical lenalidomide PK controls and before vs after colesevelam. Bioanalytical measurements for lenalidomide will be conducted on an ultra HPLC-MSMS system using an assay developed and validated by the Clinical Pharmacology Program.

8.7 Correlative analyses: Gut microbiota and bile acid analyses

Stool samples will be collected from all patients at baseline and after 12 weeks of therapy. Samples will be stored for 16S rRNA sequencing and analysis of changes in gut flora that take place before and after use of colesevelam. Microbial ecology and metagenomic analysis will be performed using accepted computational methods to infer changes in gut microbiota throughout the study. Identification and quantification of bile acid species may be explored through use of liquid chromatography/ mass spectroscopy based approaches and/or metabolomics analyses.

9.0 TREATMENT/INTERVENTION PLAN

Colesevelam is FDA approved for lowering LDL cholesterol. Several studies have revealed that diarrhea induced by bile acid malabsorption can be improved with the use of colesevelam. Thus, this indication is considered routine. Furthermore, colesevelam has been indicated for lenalidomide-associated diarrhea, however, the effects are not well studied.

9.1 Treatment regimen

Only patients with grade 1 or more (CTCAE grading) diarrhea while on lenalidomide maintenance can initiate treatment with colesevelam on the study.

The treatment arm will be:

- The starting dose of colesevelam is 1250 mg (625 mg x 2) with food once daily and dose can be increased (6 tablets max per day) based on tolerability and efficacy
- Colesevelam should be spaced out from lenalidomide and other interacting medications by at least 4 hours

- Colesevelam is given continuously and patients will be treated for up to 12 weeks on study
- Treatment will continue until drug-related toxicity, worsening diarrhea, or unimproved diarrhea at 2 weeks despite increased dosage of the study drug or for a maximum of 12 weeks of treatment
- Patients who respond can continue on colesevelam after the 12 weeks of study treatment. Coverage for colesevelam costs after the 12 weeks will not be covered by the trial but will go through patient's insurance.

9.2 Dose adjustments

Colesevelam dosing can be adjusted based on tolerability and efficacy using Table 3. The dose of colesevelam can be increase or decreased at the invesitgator's discretion based on tolerability at any timepoint as long as changes and reason are documented. If Revlimid is held, colesevelam can be held at the same time.

Table 3. Dose levels and escalation/de-escalation for colesevelam

Dose level	Dosing of Colesevelam	Dose adjustment		
0	1250 mg (2 tablets) daily	Starting dose		
1	1250 mg (2 tablets)	Increase if diarrhea remains grade 1 or		
	twice daily	higher after 2 days on each dose level		
2	1875 mg (3 tablets)	Increase if diarrhea remains grade 1 or		
	twice daily	higher after 2 days on each dose level		
-1	625 mg daily	Decrease if improvement of diarrhea		
		but emergence of side effects		

Indications for discontinuation of study medication:

- If patients cannot tolerate dose level -1 then patients should discontinue treatment and come off study
- If patient has worsening of diarrhea within the first week after starting colesevelam, they should discontinue treatment and come off study
- If the diarrhea remains grade 1 or higher after 2 weeks of treatment

The investigator may *consider* withdrawing patients from the study for any of the following reasons:

- Side effects from colesevelam
- If there is protocol violation
- Non-compliance
- Administrative reasons
- Failure to return for follow-up

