1.0 PROTOCOL SUMMARY AND/OR SCHEMA

Title

Colesevelam for lenalidomide-associated diarrhea

Primary Objective

The primary objective is to evaluate the ability of colesevelam to improve lenalidomideassociated diarrhea in patients with multiple myeloma treated with lenalidomide maintenance.

Patient population

Patients with multiple myeloma, age 18 years or older, treated with maintenance lenalidomide. Patients who experience grade 1 or worse diarrhea on lenalidomide will be treated with colesevelam.

Study design

This is a single arm, phase II trial of colesevelam for lenalidomide-associated diarrhea. Up to 40% of myeloma patients on lenalidomide maintenance experience some degree of diarrhea. There is currently no established treatment standard for patients who develop diarrhea during lenalidomide and available anti-diarrheal (i.e. loperamide, opioids) may not give optimal symptom relief. In this trial we will assess whether colesevelam, a bile acid sequestrant, can improve diarrhea associated with lenalidomide maintenance therapy in patients with grade 1 or more diarrhea. The target will be that 30% of patients with lenalidomide-associated diarrhea will have an improvement by at least 1 grade or returns to patients baseline when receiving colesevelam. A total of 25 patients will accrue on the study in a Simon's two-stage minimax design. Patients will initially be started on 1250 mg (2 x 625 mg tablets) and the dose can be increased to maximum of 6 tablets per day based on efficacy and tolerability. Treatment will be continued until drug-related toxicity, worsening of diarrhea, or diarrhea that remains grade 1 or higher at week 2. Each patient will be followed for 12 weeks after colesevelam initiation.

Secondary objectives in the study include assessment of gastrointestinal (GI) symptoms the Patient Reported Outcomes within the Common Terminology Criteria for Adverse Events (PRO-CTCAE), as well as assessment of diet using a dietary questionnaire.

Lenalidomide pharmacokinetics will be assessed in up to 15 patients to assess possible drug interactions between lenalidomide and colesevelam. In these patients, a blood sample will be drawn pre- and 2 hours post the first colesevelam dose (day 1), as well as pre- and 2 hours post colesevelam on day 8 after initiation of colesevelam. Research stool samples will be collected at baseline and after 12 weeks of treatment for microbiota and bile acid studies.

Treatment Plan

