4.0 OVERVIEW OF STUDY DESIGN/INTERVENTION

4.1 Design

This is a single institution, single arm, open label phase II trial to evaluate the efficacy of colesevelam for myeloma patients on lenalidomide maintenance who experience grade 1 or more diarrhea. Patients will be given colesevelam at a starting dose of 2 tablets (2 x 625 mg) which can be increased to up to 6 tablets per day depending on efficacy and tolerability, see dose adjustment schedule section 9.2, page 16. Patients can continue on the study until unacceptable toxicity, diarrhea that remains grade 1 or higher at week 4, worsening of diarrhea at any point, or end of study (12 weeks), whichever comes first. Each patient will be followed for a total 12 weeks.

The primary endpoint of this study is improvement of diarrhea. Response is defined as improvement by at least 1 grade according to CTCAE version 5.0 (see page 15) or returns to patients baseline when receiving colesevelam. A total of 25 patients will accrue on the study in a Simon's two-stage minimax design. In the first stage of the study, 16 patients will accrue. If 1 or fewer patients have a reduction in diarrhea severity, the study will stop due to a lack of efficacy; otherwise, an additional 9 patients will accrue. We estimate that the accrual to the study will be approximately two patients per month. The study is expected to be completed in approximately two years.

A diarrhea diary will be filled out by patients to capture frequency and consistency of bowel movements. GI symptoms will be assessed using the GI oriented PRO-CTCAE questions. Diet will be recorded at several time points to assess changes in dietary intake prior to and while on colesevelam. Stool consistency will be assessed using the Bristol Stool Form Scale. Correlative studies include pharmacokinetic (PK) evaluation of lenalidomide as well as collection of stool for studies of the GI microbiome.

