4.2 Intervention

All patients should be on maintenance single agent lenalidomide and experiencing grade 1 or higher diarrhea according to the CTCAE grading system. For treatment with colesevelam, the starting dose will be 1250 mg (2 x 625 mg) with food which can be increased to 6 tablets max per day based on efficacy and tolerability. Coleveselam should not be taken within 4 hours before or after lenalidomide and other interacting medications. All participants will be given a pill diary to record intake of colesevelam (Appendix 1). The effect of colesevelam on lenalidomide-associated diarrhea will be evaluated after 1, 2, 4, 12 weeks after start of treatment. If the diarrhea does not respond to the starting dose of colesevelam, the dose can be increased every 2 days to 2 tablets two times per day (2 x 625 mg BID) and later to 3 tablets two times per day (3 x 625 mg BID). The colesevelam dose can be decrease to 1 tablet per day if there has been improvement of diarrhea but emergence of side effects. Treatment with colesevelam will continue until drug-related toxicity, diarrhea that remains grade 1 or higher at week 2 despite dose elevations, or if worsening diarrhea occurs, or up to 12 weeks on study.

Patients will be evaluated by their physician and/or research nurse at baseline, after 1 week (+/- 2 days), after 2 weeks (+/- 2 days), after 4 weeks (+/- 7 days), and 12 weeks (+/- 7 days) for efficacy, toxicity, and compliance. The evaluations after 1, 2, and 4 weeks will preferably as office visits but can be replaced by telephone calls for sake of convenience.

Pharmacokinetics will be assessed in a subset of patients (up to 15 patients) at baseline and 8 days after start of colesevelam. All patients will be asked to participate in the PK studies and the first 15 who consent to this correlative part will be included. Research stool samples will be collected for all study participants at baseline and after 12 weeks of study.

Patients that repond to colesevelam can continue on the drug after the 12 weeks of study treatment. Coverage for colesevelam costs after the 12 weeks will not be covered by the trial but will go through patient's insurance.

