9.3 Concomitant medications

No other antidiarrheals will be allowed while on study treatment with colesevelam to evaluate efficacy accurately. If the diarrhea is worsening while on colesevelam, the patient will be

taken off study and can then start other anti-diarrheal medications. Similarly, if there is no sign of improvement after start of colesevelam despite dose escalation by 2 weeks, the patient will be taken off study and is allowed to start other anti-diarrheal medications.

Orally administered drugs that have not been tested for interaction with colesevelam, especially those with a narrow therapeutic index, should be administered at least 4 hours prior to colesevelam. Therefore, lenalidomide should be spaced out from colesevelam by 4 hours at least. In addition, the physician should monitor drug levels of the co-administered drugs. Medications with known drug interactions are listed under section 5.0 page 11.

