10.10 Table 4. Overview of time points for sampling and clinical assessment

	Baseline	Cycle 1 Day 1 (Within 14 days of baseline)	Cycle 1 Day 8 (+/-7 days)	Cycle 1 Day 15 (+/-7 days)	4 weeks/ End of Cycle 1 (+/- 14 days)	12 weeks / End of Cycle 3 (+/- 21 days)
MD/RN assessment	Visit		Visit or telephone assessment	Visit or telephone assessment	Visit or telephone assessment	Visit
Stool studies GI pathogens ^a	Xa					
Triglycerides	X					
CBC	X					X
Comp	X					X
SPEP, IFE and FLC	X					X
Stool Diary (response assessment) and Bristol Stool Scale ^b	Х		X	х	Х	Х
PRO-CTCAE	X		X	Х	Х	Х
Nutritional Survey ^c						Х
PK studies ^d		Χq	Xq			
Research stool samples ^e	Х					X

- a. Stool studies for GI pathogens should be collected prior to starting colesevelam but do not need to be resulted prior to starting Day 1 dose of colesevelam, unless infection is suspsected by the treating investigator.
- b. Response assessments (Stool diaries) will be done at Cycle 1 Day 8, Cycle 1 Day 15, end of Cycle 1 (week 4) and end of Cycle 3 (week 12). If diarrhea does not improve by at least 1 grade from baseline (using CTCAE version 5.0) or to patient's baseline bowel pattern by the end of Cycle 1 they will be removed from study.
- c. Patients will complete one nutrtional survey ("Food and Activitity Questionaire" survey will be used) and return at week 12 visit.

- d. Lenalidomide pharmacokinetics will be assessed in up to 15 patients to assess possible drug interactions between lenalidomide and colesevelam. In these patients, a blood sample will be drawn pre- and 2 hours post the first colesevelam dose (day 1), as well as pre- and 2 hours post colesevelam on day 8 after initiation of colesevelam.
- e. Research stool samples will be collected at baseline and after 12 weeks of treatment for microbiota and bile acid studies.

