13.0 CRITERIA FOR REMOVAL FROM STUDY

Patients will be informed that they have the right to withdraw from the study at any time for any reason, without prejudice to their medical care.

The investigator is *required* to withdraw patients from the study for any of the following reasons:

- If at any time a patient develops unacceptable toxicity from colesevelam
- General or specific changes in the patient's condition unacceptable for further treatment in the judgment of the investigator

• If there is no resolution of diarrhea to grade 0 at 2 weeks after the dose has been increased to dose level 2

The investigator may *consider* withdrawing patients from the study for any of the following reasons:

- Side effects from colesevelam
- If there is protocol violation
- Non-compliance
- Administrative reasons
- Failure to return for follow-up

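### The rule for stopping colesevelam for inadequate response appears in five conflicting forms, so a patient not responding at week 2 may get 2 or 4 weeks to meet a 4-week endpoint

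*Combined protocol and SAP*

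**What the plan says.** The inadequate-response rule appears in eight places and takes five forms once repeats are merged.

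1. **Residual grade 1 or higher at week 2.** Section 9.2: "If the diarrhea remains grade 1 or higher after 2 weeks of treatment". Section 1.0: "worsening of diarrhea, or diarrhea that remains grade 1 or higher at week 2". Section 4.2: "diarrhea that remains grade 1 or higher at week 2 despite dose elevations".
2. **Residual grade 1 or higher at week 4.** Section 4.1: "diarrhea that remains grade 1 or higher at week 4, worsening of diarrhea at any point".
3. **No improvement at 2 weeks.** Section 9.1: "unimproved diarrhea at 2 weeks despite increased dosage of the study drug". Section 9.3: "if there is no sign of improvement after start of colesevelam despite dose escalation by 2 weeks"; such a patient comes off study and may start other antidiarrheals.
4. **No response by week 4.** Table 4 note b covers patients without a 1-grade improvement "or to patient's baseline bowel pattern by the end of Cycle 1 they will be removed from study".
5. **Not grade 0 two weeks after reaching the top dose.** Section 13.0, as a mandatory withdrawal: "If there is no resolution of diarrhea to grade 0 at 2 weeks after the dose has been increased to dose level 2".

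Section 2.0 sets the primary endpoint at 4 weeks of treatment. Section 14.0 counts success at any point in those 4 weeks and classes removal for worsening, lack of improvement or drug-related toxicity within them as treatment failure.

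**The concern.** A clinician cannot comply with all of these sections at once, and no section is given precedence. The choice of section decides how long a patient who is not yet responding has on drug to meet the primary endpoint. A patient stopped at week 2 cannot respond on colesevelam in weeks 3 to 4 and is scored a failure, although the endpoint is meant to count a response in that period.

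The forms also disagree on the criterion. A patient who goes from grade 3 to grade 1 by week 2 is a responder under Sections 2.0, 4.1 and 12.0 and stays on under forms 3 and 4, but must stop the drug under form 1.

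The Section 9.2 bullet adds a further gap: it stops medication without saying whether the patient also comes off study, while the two bullets above it do say so.

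At stake is the power of a 25-patient trial in which 5 responses decide the result. The number of responses observed would depend partly on which page was followed.

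**Working it through.** **Which forms conflict**

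| Form | Criterion for stopping | When | Where |
|---|---|---|---|
| 1 | Grade 1 or higher | Week 2 | 1.0, 4.2, 9.2 |
| 2 | Grade 1 or higher | Week 4 | 4.1 |
| 3 | No improvement | Week 2 | 9.1, 9.3 |
| 4 | No 1-grade improvement or return to baseline | Week 4 | Table 4 note b |
| 5 | Not grade 0 | 2 weeks after dose level 2 | 13.0 |

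- Forms 1 and 2 share a criterion and differ on the week, so they contradict each other directly.
- Form 1 contradicts forms 3 and 4 on the criterion: it stops a patient who has improved but is not at grade 0.
- Forms 3 and 4 could run in sequence (no improvement at week 2, then no response at week 4).
- Form 5 has its own clock. With 2-day steps and a day 1 start, level 1 comes on day 3 and level 2 on day 5; 5 + 14 gives day 19 at the earliest.

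**The plan's own figures (Section 14.0)**

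Inputs: 16 patients in stage 1, stop if 1 or fewer respond; 9 more; promising if more than 4 of 25 respond; rates 10% and 30%; both error limits 0.10.

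The probability of declaring the treatment promising at true rate p is

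P(p) = Σ over x = 2 to 16 of Pr[Bin(16, p) = x] × Pr[Bin(9, p) ≥ 5 − x].

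- P(0.10) = 0.095 (type I error).
- P(0.30) = 0.903 (power).
- A search for the smallest total sample size meeting both limits returns this same design, so the stated design reproduces.

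**Effect of a week 2 stop**

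Let L be the share of 4-week responders whose first response would come after week 2. The documents do not give L; the values below are assumptions. The true 4-week rate is taken as 30%.

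- Form 1 for every patient: observable rate = 0.30 × (1 − L).
- Half the patients under form 1 and half under a week 4 form: observable rate = 0.30 × (1 − L/2).

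| L | Rate, form 1 for all | Power | Stage 1 futility stop | Rate, half and half | Power |
|---|---|---|---|---|---|
| 0 | 0.30 | 0.903 | 0.026 | 0.30 | 0.903 |
| 10% | 0.27 | 0.837 | 0.045 | 0.285 | 0.873 |
| 20% | 0.24 | 0.742 | 0.075 | 0.27 | 0.837 |
| 30% | 0.21 | 0.617 | 0.121 | 0.255 | 0.793 |

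Under week 4 forms alone, power stays at 0.903. Form 3 lies between, because it stops fewer patients at week 2 than form 1.

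**Type I error.** With a true 4-week rate of 10% and form 1 for all, L of 10%, 20% and 30% gives rates of 0.09, 0.08 and 0.07, and the false-positive probability falls from 0.095 to 0.067, 0.044 and 0.027.

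**The case against.** The strongest reply has four parts.

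- **The meaning of 30%.** Section 14.0 already scores early removals as failures, so the 10% and 30% rates can be read as rates under the protocol's own removal rules. A week 2 stop applied consistently would then leave power at 0.903. The documents do not say which reading is meant. This would answer the power point if there were one removal rule, but the rules contradict each other, so there is no defined rate to appeal to.
- **The late share may be small.** The maximum dose can be reached by about day 5, and after week 2 only the week 4 visit remains in the window. With 10% late responders and mixed practice, power is 0.873 against 0.903, a modest loss. The 0.617 figure needs both a 30% late share and form 1 for everyone. The loss also shrinks if the drug works better than planned: at an assumed true rate of 40% with 20% late, the observable rate is 0.40 × 0.80 = 0.32 and power is 0.934. All of this stands as a limit on the size. Against it, escalation is permitted rather than required, and Section 9.2 lets colesevelam be held with lenalidomide without saying that the 2-week clock pauses.
- **Early responses still count.** Under the 1-grade definition, the patient who goes from grade 3 to grade 1 is already a responder when stopped. That is right; the loss for that patient is continued treatment and week 12 data. It reaches the primary endpoint only under the grade 0 wording in Section 14.0.
- **A week 2 stop is a legitimate design,** and five of the eight places use it. It spares unimproved patients two more weeks without other antidiarrheals. This is also fair, and is why the fix below leaves that option open.

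**Conclusion.** The concern holds and must be fixed. The contradiction does not depend on any assumption: week 2 and week 4 are both given for residual grade 1 or higher, and residual grade and absence of improvement are both given as the criterion, with nothing to say which governs. Two patients with the same course can therefore have different chances of being counted as responders.

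The size does depend on assumptions. With a true 4-week rate of 30% and late shares of 10% to 30%, power is 0.84 to 0.62 if the week 2 residual-grade rule is applied to everyone, and 0.87 to 0.79 under an even mix of rules. The planned 0.903 barely exceeds the 0.90 target, so even the mildest of these cases falls below it. The bias is conservative: the risk is missing a useful treatment, and the false-positive risk does not rise.

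**What to change.** Align Sections 1.0, 4.1, 4.2, 9.1, 9.2, 9.3 and 13.0 and Table 4 note b to one rule that matches the endpoint.

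- **Preferred:** adopt the existing Table 4 note b rule. Remove a patient at week 4 if the primary-endpoint definition of response has not been met, with earlier removal only for worsening or toxicity.
- **Alternative:** if a week 2 stop is wanted, end the primary-endpoint window at week 2 and state the 10% and 30% rates for that window.
- **In either case:** state that a patient who has met the response definition is not removed for residual grade 1 or higher, and say in Section 9.2 whether stopping medication also means coming off study.

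The cost is a protocol amendment to align wording, with no new visits. The downside of the week 4 rule is that non-responders may spend up to two more weeks on colesevelam without other antidiarrheals.
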